Effect of Professional Prophylaxis on Clinical Parameters and Patient Comfort:

Randomized Clinical Trial

12/01/2022

Study Protocol:

After the initial evaluation of the participants and their inclusion in the study, the participants were randomized in blocks into group A where a conventional protocol was used in quadrants I and III and the test protocol in quadrants II and IV, and group B where a conventional protocol was used in quadrants II and IV and the test protocol in quadrants I and III and III.

The observations were made at three different times: baseline, one week after the intervention, and three weeks after the intervention. (Figure 1)

The clinical assessment of each participant was performed using the the Ainamo & Bay gingival bleeding index (GBI), the O'Leary plaque control record (PCR) and the Silness and Löe plaque index (PI). (26–28) The primary outcome variable of the study was the Gingival Bleeding Index (GBI) with the Plaque Index (PI) as a secondary outcome variable.

Hard and soft deposits were removed according to the protocol assigned in one appointment performed by the principal investigator the day after the first data collection. The control protocol consisted of mechanical scaling with Woodpecker® scaler (Guilin, Guangxi, 541004 P.R.China) at power 1, followed by stain removal and polishing with R&S RUBBER DOME (R&S® Dental products [name]) with Prophy Paste CCS® polishing paste RDA 250 (Directa AB [name]) at a speed of 10,000 rotations per minute.

The test protocol consisted in an assessment of the periodontal status following the application of the plaque discloser (Biofilm Discloser, [name] & Co KG 64673 Zwingenberg - Germany), followed by oral hygiene instructions and biofilm removal with an erythritol jet (Airflow Plus Powder®, Electro Medical Systems S.A.), [name]) with the Airflow Prophylaxis Master® device (Electro Medical Systems S.A., [name]). The jet stream was used at a power of 3 and the irrigation at a power of 10. Calculus removal was then performed with the piezon scaller of the same device using a PS scaler tip (Electro Medical Systems® S.A., [name]).

The first follow-up assessment (T1) was performed one week after the intervention, and the second follow-up assessment (T2) was performed 3 weeks after the intervention performed by the same research assistant that performed the initial assessment (T0). indeces The precision and accuracy of the data collection was ensured by calibrating the instruments used and the investigators to minimize and control possible measurement errors. The assistant investigator underwent calibration before the start of the study to train the indeces, followed by a discussion of the criteria with the principal investigator.

After the appointment the participant rated comfort using a Visual Analog Scale measured on a Likert scale of 0 to 10 for each quadrant.

Statistical Analysis Plan:

The sample size was calculated for a power of 80% to allow the study to detect a difference at the 0.05 significance level when the true difference between treatments is 0.5 units.

Data were entered into SPSS® software (Statistical Package for the Social Sciences, IBM, Armonk, NY, USA), version 27.

Descriptive and inferential statistics were performed to evaluate the results of the two protocols, with a significance level of 5%. The mean values and standard deviations of the clinical parameters were calculated per protocol and per study group, and for the 3

evaluation moments: for the initial moment (T0), for the evaluation at 1 week (T1), and for the final evaluation (T2).

Comparisons between evaluation moments in each protocol were evaluated using the nonparametric Wilcoxon test for paired samples.

The Mann-Whitney U test was used to analyze differences between protocols. The Friedman test was used to analyze the differences between the different evaluation periods.

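### The between-protocol test ignores both the randomised quadrant pattern (A/B) and the fact that each mouth receives both protocols; one within-mouth contrast compared between A and B repairs both

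*Combined protocol and SAP*

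**What the plan says.** Study Protocol section: "the participants were randomized in blocks into group A where a conventional protocol was used in quadrants I and III", with the test protocol in II and IV, and "group B where a conventional protocol was used in quadrants II and IV", with the test protocol in the other pair. (The group B sentence repeats a quadrant number at its end; I read it as the mirror of group A.) Each participant therefore contributes both protocols, and chance decides only which diagonal pair gets which.

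Statistical Analysis Plan section, on the use of group: "The mean values and standard deviations of the clinical parameters were calculated per protocol and per study group". The named tests are:

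- Over time within a protocol: "Comparisons between evaluation moments in each protocol were evaluated using the nonparametric Wilcoxon test for paired samples".
- Across the three visits: "The Friedman test was used to analyze the differences between the different evaluation periods".
- Between protocols: "The Mann-Whitney U test was used to analyze differences between protocols".

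No named test contains group or quadrant pair, and the between-protocol test has no participant term.

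**The concern.** The A/B pattern plays the part that sequence plays in a two-period crossover: it allows the protocol effect to be separated from any difference between the two quadrant pairs. The plan randomises this factor and then leaves it out of inference. It also uses a test for independent samples on two sets of values from the same mouths. The Wilcoxon test is paired, but over visits within one protocol, so it does not supply the missing within-mouth comparison of protocols.

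At stake is the chance of detecting a real difference between protocols. A test that is too conservative in a split-mouth trial can report no difference when the data would have shown one.

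**Working it through.** **The plan's own figure.** The SAP states 80% power at the 0.05 level for a difference of 0.5 units. It gives no sample size, SD or within-mouth correlation, so this cannot be reproduced. For a two-sided test, n = (SD of difference × (1.960 + 0.842) / 0.5)² gives 8, 32 or 126 mouths for an SD of the within-mouth difference of 0.5, 1 or 2. Two independent samples would need 16, 63 or 252 per protocol at a score SD of 0.5, 1 or 2.

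**Assumptions for what follows (none in the documents).** 32 mouths, 16 per group; one value per protocol per mouth; score SD 1 and correlation 0.5, so the SD of the within-mouth difference is √(2 × (1 − 0.5)) = 1; protocol effect δ = 0.5. Let d be the mean in II+IV minus the mean in I+III under the same protocol, in units of that SD.

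**Step 1: where d goes.** Test minus conventional has mean δ + d in group A and δ − d in group B. With equal groups the pooled mean is δ, so there is no bias. The pooled variance is 1 + d²: up 6% at d = 0.25 and 25% at d = 0.5.

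**Step 2: effect on a pooled paired test.** The estimate itself is no noisier, because +d and −d cancel; only its estimated standard error is too large. Starting from 80% power (1.960 + 0.842 = 2.802), power is Φ(2.802 − 1.96√(1 + d²)):

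- d = 0.25: Φ(2.802 − 2.020) = 0.78
- d = 0.5: Φ(2.802 − 2.191) = 0.73

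The true type I error is 2(1 − Φ(1.96√(1 + d²))): 0.043 and 0.028.

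**Step 3: the contrast that uses group.** X = (I+III) − (II+IV) has mean −δ − d in A and δ − d in B. The difference between groups is 2δ in absolute value, and d drops out. Signal over standard error is 1/√(1/16 + 1/16) = 2.83, the same as 0.5/(1/√32) = 2.83 for the paired difference. Estimating d therefore costs almost nothing.

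**Step 4: simulated power** (4000 runs; Monte Carlo error just under one point):

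| d | Planned Mann-Whitney between protocols | Signed-rank on within-mouth difference, group ignored | Mann-Whitney on X, A versus B |
|---|---|---|---|
| 0 | 0.49 | 0.77 | 0.76 |
| 0.25 | 0.46 | 0.73 | 0.75 |
| 0.5 | 0.45 | 0.68 | 0.76 |
| 1.0 | 0.34 | 0.42 | 0.74 |

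With no protocol effect, the test on X rejects in 0.04–0.05 of runs at every d. The planned test rejects in about 0.006 at d = 0, far below its nominal 5%.

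**Step 5: splitting the gain.** At d = 0 the move from the planned test to X (about 0.48–0.49 to 0.76) is entirely due to pairing. The part due to group is the gap between the last two columns. Across repeat simulations of the same set-up it is about −1 point at d = 0, 0–1 at d = 0.25 and about 7 (6–8) at d = 0.5.

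**Step 6: dependence on the correlation** (d = 0, score SD 1). Planned test against X: 0.48 and 0.47 at correlation 0; 0.49 and 0.61 at 0.3; 0.47 and 0.99 at 0.8.

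**Step 7: unequal groups.** Bias is d(nA − nB)/N: 0.06d at 17:15 (2/32) and 0.125d at 18:14 (4/32).

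**The case against.** The strongest reply is that the quadrant-pair effect may hardly exist. Under the usual quadrant numbering each pair holds one upper and one lower, one right and one left quadrant, so main effects of jaw and side cancel. The documents give no evidence of any remaining difference, and with d at 0.25 or below, using group gains nothing worth having. That stands, and it is why pairing carries most of the argument.

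Some stronger readings are tempting, but the documents do not support them:

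- *A reader might infer that the protocol comparison is biased.* With equal groups it is not. Participants are randomised in blocks, so the groups should be close in size, and a 17:15 split at d = 0.5 gives only about 0.03 SD.
- *A reader might blame the whole power loss on ignoring group.* In the planned unpaired test, d adds only d²/4 to the variance within each protocol. In the table above that costs 3–4 points up to d = 0.5, and other runs gave less at some values.
- *A reader might treat d as sampling noise*, using Φ(2.802/√(1 + d²) − 1.96), and get 0.71 at d = 0.5. With equal groups the estimate is unaffected, and the value is 0.73.
- *A reader might say that any analysis pooling A and B departs from the randomisation.* For a paired signed-rank test this is wrong: if the protocols do not differ, assignment to A or B only flips the sign of each mouth's difference, which is that test's reference distribution. The charge fits the unpaired test.
- *A reader might single out comfort because it has no baseline rating.* The SAP states no baseline adjustment in the between-protocol test for any outcome, so comfort is not a special case.

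Nor can the Mann-Whitney test be rescued by reading it as a comparison of groups A and B, since the text names protocols.

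**Conclusion.** The point holds as a matter of efficiency and of matching the analysis to the design. The randomised factor enters no named test, and the between-protocol test ignores that both protocols share a mouth. Under the stated assumptions the planned test has power of about 0.48 where about 0.76 is available. Nearly all of the gap is lost pairing, and its size depends on the within-mouth correlation, being nil at zero correlation. Ignoring group adds to the loss only if the quadrant pairs differ appreciably, and that difference is unknown and may be small. The consequence is a conservative test, not a false-positive problem and, with near-equal groups, not a material bias.

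**What to change.** Replace the between-protocol sentence of the SAP with the following. For each participant, and at each visit where protocols are compared, form X = value in quadrants I+III minus value in II+IV, giving one number per mouth. Compare X between randomised groups A and B with the Mann-Whitney U test, and state that the location shift is, in absolute value, twice the protocol effect. Alternatively, model each participant's test-minus-conventional difference with an A/B term coded +1/−1. Apply the same analysis to GBI, PI, PCR and comfort. The Wilcoxon and Friedman tests can stay as descriptions of change over time.

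This keeps the named test, makes its two samples independent participants, removes d and restores the pairing. The cost is SAP wording and about one point of power if the quadrant pairs do not differ. No new data are needed, because the contrast uses only outcomes separated by quadrant, which the comparison of protocols already requires.

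### The primary outcome, GBI, has no deciding visit: the plan does not say whether week 1 (T1) or week 3 (T2) settles the comparison between protocols

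*Combined protocol and SAP*

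**What the plan says.** The Study Protocol section names the outcome without a time point: "The primary outcome variable of the study was the Gingival Bleeding Index (GBI) with the Plaque Index (PI) as a secondary outcome variable". It lists the times without ranking them: "The observations were made at three different times: baseline, one week after the intervention, and three weeks after the intervention". The text just before the Statistical Analysis Plan heading defines the two follow-ups: "The first follow-up assessment (T1) was performed one week after the intervention, and the second follow-up assessment (T2) was performed 3 weeks after the intervention".

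In the Statistical Analysis Plan, the between-protocol test is given in one sentence: "The Mann-Whitney U test was used to analyze differences between protocols". The power statement aims "to detect a difference at the 0.05 significance level when the true difference between treatments is 0.5 units", with 80% power, and names no outcome or visit. The overall significance level is 5%. No sample size, standard deviation, sidedness or multiplicity rule is given.

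**The concern.** A primary outcome measured at two follow-up visits becomes a primary result only once one visit, or a rule combining both, is named. Here the plan would produce GBI at both visits, and a reader could not tell which comparison was confirmatory. If one visit reached significance and the other did not, either could be put forward as the trial's answer. Once the data have been seen, the choice cannot be made without risk of bias.

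The 0.5-unit difference in the power statement is also left without an anchor. The standard deviation needed to check it depends on the outcome and visit it refers to, and neither is stated.

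**Working it through.** **1. Does any sentence settle the visit?**
- The Mann-Whitney sentence names no outcome and no visit.
- The power sentence names no outcome and no visit.
- T2 is called final only in the list of times at which means and standard deviations are summarised: "evaluation moments: for the initial moment (T0), for the evaluation at 1 week (T1), and for the final evaluation (T2". T0 and T1 are labelled in the same list, so the word gives chronology, not rank.
- "Comparisons between evaluation moments in each protocol were evaluated using the nonparametric Wilcoxon test for paired samples". This compares visits inside one protocol.
- "The Friedman test was used to analyze the differences between the different evaluation periods". This compares periods, not protocols.
- Figure 1 is not shown. It is cited for the observation times, and no text gives it a role in choosing a primary visit.

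No sentence settles it. There is no figure in the plan to reproduce, because no sample size or standard deviation is given.

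**2. False-positive chance if either visit may count, with a valid test at each.**
Input from the plan: 5% level, taken as two-sided (critical value 1.96). Assumed: the correlation ρ between the T1 and T2 test statistics.
Formula: 1 − P(|Z1| < 1.96 and |Z2| < 1.96), bivariate normal.
- ρ = 0: 1 − 0.95² = 0.0975
- ρ = 0.5: 0.0907
- ρ = 0.7: 0.0835
- ρ = 0.9: 0.0704

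**3. The same chance under the planned Mann-Whitney test.**
Each participant receives both protocols, in different quadrants. An unpaired test ignores the positive correlation between the two halves of a mouth and so rejects too rarely when there is no effect. Simulation under no effect: normal data, one value per half-mouth, 30 participants (assumed), 40,000 replicates.

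| Within-participant correlation (assumed) | T1 or T2 significant, T1-T2 correlation 0.5 / 0.7 / 0.9 |
|---|---|
| 0.1 | 7.4% / 6.7% / 5.6% |
| 0.2 | 5.5% / 5.1% / 4.5% |
| 0.3 | 3.9% / 3.7% / 3.2% |
| 0.5 | 1.5% / 1.5% / 1.3% |
| 0.7 | about 0.2% throughout |

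**4. Illustration: how often the visits would disagree.**
Assumed: equal true effect at both visits, 80% power at each, 30 participants, normal data, 20,000 replicates. Share of trials with exactly one of T1 and T2 at p < 0.05, over within-participant correlations 0.2 to 0.7 and both the Mann-Whitney and signed-rank tests:
- T1-T2 correlation 0.9: about 11-12%
- 0.7: about 18-19%
- 0.5: about 23-24%

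**5. Power at the first Holm step.**
A comparison with 80% power at two-sided 5% has expected z = 1.960 + 0.842 = 2.802. At 2.5% the critical value is 2.241. Power = Φ(2.802 − 2.241) = Φ(0.561), about 71%.

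**The case against.** **Under the planned test there is little or no excess error.** This stands. By the table above, the either-visit rate is about 5% or less once the within-participant correlation reaches about 0.2. A reader might infer that the plan as written inflates the type I error; the documents do not support that, since they give no correlation. The 7.0-9.75% range belongs to a valid paired test, which the plan does not use for this comparison. But the conservatism is a side effect of ignoring the pairing, and it disappears when the pairing is corrected.

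**Disagreement in 11-24% of trials is not an error rate.** This also stands. Two visits would disagree that often whether or not one is named; naming one only says beforehand which result counts. The figure rests on 80% power at each visit, which the plan does not claim.

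**Both visits would be seen anyway.** The plan does summarise all three times. That limits concealment but does not say which visit is confirmatory.

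**T2 is plainly the main visit.** It may be what the investigators intend, but nothing in the text ranks it above T1.

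**Value against change from T0.** A reader might count four open contrasts: two visits, each as a value or a change. The documents never mention a change score, and the natural reading is visit values. It is enough to state this explicitly.

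**The text is in the past tense.** That makes it doubtful that the choice can still be made before analysis, but does not prove that the data were analysed. Nor do the documents show that a visit was picked after seeing results; they show only that the plan leaves room for it.

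**Conclusion.** The point holds as a gap in the plan: GBI is primary, but no visit decides the between-protocol comparison. This conclusion rests on the text alone. How much it matters for error depends on the test. Two looks with a valid paired 5% test give 7.0-9.75%. The planned Mann-Whitney test gives about 6-7% at within-participant correlation 0.1, about 5% at 0.2, and less above that. The correlations are assumptions throughout, and so is the sample size of 30 in the simulations. Inflation under the plan as written is not established. What is established is that the trial could not say beforehand which GBI result would count. The plan should be amended on this point.

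**What to change.** Before analysis, add one paragraph to the Statistical Analysis Plan that does the following:
- Name one visit, chosen and justified by the investigators, as the primary between-protocol comparison of GBI at two-sided 5%. Either visit can be chosen, with a reason.
- State that the GBI value at that visit is compared.
- Test the other visit at 5% only if the first is significant.
- Tie the 0.5-unit difference to this comparison.

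Apply it with the Wilcoxon signed-rank test on one difference per participant, test half minus conventional half. This corrects a separate error, the use of an unpaired test on paired halves, and should be labelled as a separate edit. The visit must be named whichever test is used. The standing of PCR and comfort need not change.

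**Cost.** The ordered scheme needs no extra participants on account of multiplicity, because the first-ranked visit keeps the full 5%. The downside is that an effect seen only at the second-ranked visit cannot be claimed as confirmatory.

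**If the data have already been examined,** report GBI values at both visits with Holm adjustment and state that neither visit was pre-specified. This has a price: Holm tests the smaller p-value at 2.5%, where a comparison with 80% power at 5% has about 71%. Some of that can be regained through the other visit or the second step.

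### Patient comfort is in the trial's title but has no outcome rank and no named paired analysis, and the plan does not say which outcomes are confirmatory

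*Combined protocol and SAP*

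**What the plan says.** The title sets two questions: "Effect of Professional Prophylaxis on Clinical Parameters and Patient Comfort". The outcomes paragraph under Study Protocol lists three clinical indices (GBI, PCR and PI) and then ranks two of them: "The primary outcome variable of the study was the Gingival Bleeding Index (GBI) with the Plaque Index (PI) as a secondary outcome variable". PCR is left unranked and comfort is not mentioned there.

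Comfort appears once more, in the last sentence before the Statistical Analysis Plan heading: "After the appointment the participant rated comfort using a Visual Analog Scale measured on a Likert scale of 0 to 10 for each quadrant". Under the allocation in Study Protocol, each participant has two quadrants on the conventional protocol and two on the test protocol, so each participant rates both.

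The SAP does not name comfort. Its descriptive summaries are for the clinical indices at T0, T1 and T2: "The mean values and standard deviations of the clinical parameters were calculated per protocol and per study group". The paired Wilcoxon test is assigned to comparisons between visits within a protocol, and Friedman to differences across visits. Protocol comparisons get one sentence: "The Mann-Whitney U test was used to analyze differences between protocols". No outcome or visit is attached to it. The significance level is stated once, at 5%, for all inference on the two protocols. No test order, adjustment or exploratory label appears.

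**The concern.** Comfort is half of the title question, so readers will take a comfort p-value as a conclusion of the trial. The plan does not say what standing that p-value has, which comparison produces it, or how four quadrant ratings become one comparison.

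Two things are at stake. The first is interpretation. If GBI shows nothing, the plan does not stop a nominal p<0.05 on PI, PCR or comfort from being put forward in its place. Plaque has two chances, because it is measured by both PI and PCR. The second is efficiency. If the protocol-difference test is applied to comfort as written, it treats two sets of ratings from the same people as independent samples and discards the main advantage of a split-mouth design.

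**Working it through.** The documents give no familywise error figure, sample size, standard deviation or correlation, so there is no stated figure to reproduce. The only design inputs are 80% power, a 0.05 level and a 0.5-unit difference with no outcome attached.

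**Step 1. Which SAP test could apply to comfort?**

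| SAP element | Applies to comfort? |
|---|---|
| Means and SDs of the clinical indices at T0, T1, T2 | No: comfort is not a clinical index and is rated once |
| Paired Wilcoxon between visits | No: there is one rating occasion |
| Friedman across visits | No: same reason |
| Mann-Whitney between protocols | Possibly: no outcome is named, but it ignores the pairing |

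**Step 2. Chance of a false claim among the three non-primary outcomes (PI, PCR, comfort).** Assume all nulls are true and each outcome has one two-sided test at a valid 5%.

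- Independent tests: 1 − 0.95³ = 1 − 0.8574 = 14.3%.
- Upper bound: 3 × 0.05 = 15%.
- Equally correlated normal test statistics (correlations assumed; 400,000 draws): 13.6% at 0.3, 12.5% at 0.5, 9.8% at 0.8.

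With GBI counted as a fourth test: 1 − 0.95⁴ = 18.5% if independent, 15.6% at 0.5 and 11.4% at 0.8. The choice between T1 and T2 is a separate matter and is not counted.

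**Step 3. What the SAP's own test does to these figures.** Simulation with one value per protocol per participant, within-person correlation of 0.3 or 0.6 and n of 20 or 30 (all assumed), Mann-Whitney at nominal 5%:

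| n | Correlation 0.3 | Correlation 0.6 |
|---|---|---|
| 20 | 1.9% | 0.4% |
| 30 | 2.2% | 0.3% |

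Taking 0.3% to 2% per test, three independent tests give 1 − 0.997³ = 0.9% up to 1 − 0.98³ = 5.9%. Most of the inflation in Step 2 could therefore be absent if Mann-Whitney is used this way. The simulation does not cover quadrant ratings entered as separate observations, and the SAP does not say which unit is used.

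**Step 4. What ignoring the pairing costs.** Under the same assumptions, with a true effect of 0.5 SD (assumed), power is about 26–44% with Mann-Whitney and about 41–83% with the paired Wilcoxon test.

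**Step 5. Would Holm within a secondary family be enough?** Suppose GBI is tested at 5% and, separately, comfort and PI by Holm at 5%. With all nulls true and tests independent, no false claim requires GBI p ≥ 0.05 and both secondary p-values ≥ 0.025:

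1 − 0.95 × 0.975² = 1 − 0.95 × 0.9506 = 9.7%.

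At an assumed correlation of 0.5 it is 8.7%. A comfort claim after a null GBI also remains possible. If the secondary tests are made only after GBI is significant at 5%, a false claim under the global null requires a false GBI result first, so the overall chance stays at or below 5%.

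**The case against.** The strongest reply is that the plan already names a single primary outcome, which is the main protection, and that unadjusted secondary outcomes are acceptable when reported as exploratory. That stands as a principle, and it is why no particular multiplicity procedure is compelled here. But the plan contains no such label, and comfort is a title-level aim.

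A second reply is that the 5% level and the Mann-Whitney sentence are general and can be read as covering comfort. That is fair. A reader might infer that comfort has no error control at all. The documents do not support that: a nominal per-test 5% exists. What is missing is familywise control and a named comparison.

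A reader might also infer that any comfort finding would be unplanned. That does not follow either. The title names comfort, and the protocol fixes who rates it, when, on what scale and for which unit. The wording that makes PI a secondary outcome need not be an exhaustive list. Comfort is planned but unranked, with no dedicated analysis.

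A third reply is that Mann-Whitney on paired data is conservative, so the real false-claim rate is below 14%. This also stands, under the assumptions in Step 3. The conservatism comes from a mismatched test and is paid for in power, and it does not settle which outcomes may support a claim.

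**Conclusion.** The concern holds in a limited form. Comfort is a stated aim with no outcome rank and no named analysis, and the one SAP test that could reach it ignores the within-participant pairing. Nothing says whether PI, PCR and comfort are confirmatory or supportive.

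With one valid 5% test each, the chance of at least one false claim among the three is 14% if independent, 12.5% at correlation 0.5 and 9.8% at 0.8. The correlations are assumptions, and independence is doubtful for two indices of the same plaque. These figures should not be read as the error rate of the plan as written, because Mann-Whitney at participant level would probably run well below 5% per test. The firmer loss is in power for comfort: roughly 26–44% against 41–83% in the assumed scenarios.

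This should be corrected because it affects how a title-level result is read. It does not undermine the choice of GBI as primary.

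**What to change.** In the outcomes paragraph and the SAP:

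1. Name comfort as a secondary outcome.
2. Define one comparison per participant: the mean rating of the two test quadrants minus the mean rating of the two conventional quadrants. Analyse it with a paired test such as the Wilcoxon signed-rank test, which the SAP already uses for visit comparisons.
3. State that GBI alone carries the confirmatory claim at 5%, and that PI, PCR and comfort are supportive and cannot replace a null GBI.

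If a confirmatory comfort claim is wanted, test comfort only after GBI is significant. Holm within the secondary family alone would leave the overall chance of a false claim at about 9–10% (Step 5, correlations 0 to 0.5). Ranking PCR below PI, or making it descriptive, is a reasonable option but a matter of judgement.

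The cost is a few sentences and no new data. The downside is that a comfort or plaque result cannot stand as the trial's main conclusion if GBI is null. If the data have already been analysed, disclose the ranking as post hoc and report comfort as exploratory.

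### The plan sets no treatment sequence and rates comfort only after the appointment, so treatment order may be confounded with protocol in the comfort comparison

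*Combined protocol and SAP*

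**What the plan says.** The Study Protocol section describes a split-mouth design. Allocation is by quadrant pair: "the participants were randomized in blocks into group A where a conventional protocol was used in quadrants I and III"; the other two quadrants there receive the test protocol. The second group mirrors this: "group B where a conventional protocol was used in quadrants II and IV and the test protocol in quadrants I and III". Both protocols are given at the same visit: "Hard and soft deposits were removed according to the protocol assigned in one appointment performed by the principal investigator". The last paragraph of that section gives the comfort measurement: "After the appointment the participant rated comfort using a Visual Analog Scale measured on a Likert scale of 0 to 10 for each quadrant".

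The title puts comfort alongside the clinical measures: "Effect of Professional Prophylaxis on Clinical Parameters and Patient Comfort". The Study Protocol section, however, names the gingival bleeding index as primary and the plaque index as secondary, and gives comfort no rank. The Statistical Analysis Plan names no analysis for comfort. Its only comparison between protocols is general: "The Mann-Whitney U test was used to analyze differences between protocols".

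Neither section gives a quadrant sequence or a protocol sequence, says that sequence is randomised or recorded, or includes order in an analysis.

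**The concern.** Comfort during a full-mouth cleaning may depend on when a quadrant is treated as well as how. Fatigue, growing sensitivity, or getting used to the procedure could each move the score of later quadrants. In a split-mouth trial with one appointment, that matters if one protocol tends to come later than the other.

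The A/B randomisation exchanges the quadrants between protocols. It does not by itself exchange the order of the protocols. The plan as written therefore permits an operator to complete the same protocol first in every participant. An order effect would then be reported as a protocol effect on one of the two results announced in the title. The point concerns comfort only; it makes no claim about the bleeding or plaque indices.

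**Working it through.** **Inputs from the documents.** Group A: control in I and III, test in II and IV. Group B: the reverse. One appointment and one operator. One comfort score per quadrant, given afterwards.

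**Not in the documents.** Treatment sequence, A:B ratio, number of participants, the SD of comfort, and the size of any order effect. There is no comfort figure to reproduce. The sample-size statement (80% power, 0.05 level, 0.5 units) names neither outcome nor SD, so it cannot be tied to comfort.

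**Step 1: one common quadrant order.** Assume each later position shifts the score by e points. The order contribution to test minus control is

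e x (mean position of test quadrants - mean position of control quadrants).

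For the order I, II, III, IV:

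- Group A: control in positions 1 and 3 (mean 2), test in 2 and 4 (mean 3), giving +1e.
- Group B: the reverse, giving -1e.
- Average with 1:1 allocation: (1e - 1e)/2 = 0.

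This is general. In any common order, the quadrant at each position is control in one group and test in the other, so the contribution in B is minus that in A. Enumerating all 24 orders gives an average of 0 each time. With a share a of participants in group A, the order I to IV leaves a(e) + (1-a)(-e) = (2a-1)e; for example, a = 0.6 leaves 0.2e.

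**Step 2: one protocol completed before the other.**

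- Control first: control in positions 1 and 2 (mean 1.5), test in 3 and 4 (mean 3.5), giving +2e in A and +2e in B.
- Test first: -2e in both groups.

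The sign is the same in A and B, so the allocation cancels nothing. Write d = 2e for the whole effect of going second rather than first.

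**Step 3: a mixture.** If control goes first in a share p of participants, the bias is

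p(d) + (1-p)(-d) = (2p-1)d.

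With e assumed to be 0.25 or 0.5 point per position, d is 0.5 or 1.0 point:

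| Share p with control first | Bias, d = 0.5 | Bias, d = 1.0 |
|---|---|---|
| 0.50 | 0 | 0 |
| 0.75 | 0.25 | 0.50 |
| 1.00 | 0.50 | 1.00 |

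For p below 0.50 the sign reverses.

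**Step 4: can analysis repair it?** Let t be the true protocol effect. The mean difference is t + d in participants who start with control and t - d in those who start with test; half the sum is t. So if both orders occur and are recorded, t can be estimated, provided that the choice of order was unrelated to the participant. If p = 1, only t + d is observed and the two parts cannot be separated.

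**Step 5: which case applies?** The documents do not say. The control protocol uses one scaler, then a rubber dome and paste. The test protocol uses a discloser, instructions, an erythritol jet and the scaler of another device. Treating I, II, III, IV means three changes of protocol; finishing one protocol first means one. That makes Step 2 plausible on grounds of convenience, but it is an inference.

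**The case against.** The strongest reply is that the mirror allocation already does the balancing: under any quadrant order common to all participants, with equal groups, the average order bias is zero. That is correct, and it rules out the inference that nothing in the design balances order. What remains is that the plan states neither a common order nor the A:B ratio, so the balance is available but not secured.

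Three other stronger readings are also unsupported.

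- A reader might infer that one protocol was in fact always given first and that the comparison is confounded. No text says so; complete confounding follows only if that was the practice in every participant.
- A reader might infer that scoring from memory biases the result. Recall alone favours neither protocol unless it is tied to order or to knowledge of the treatment. Rating all four quadrants together at the end allows direct comparison and is a legitimate choice.
- A reader might turn the bias into a false-positive rate. The documents give no number of participants or SD for this, and the rate depends on the test. Rates from a paired test do not carry over to the unpaired Mann-Whitney test, which rejects less often for the same bias when a participant's scores are positively correlated.

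It is also fair to say that comfort is unranked. This limits the weight of the point but does not remove it, because the title presents comfort as a result of the trial.

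**Conclusion.** The concern holds in conditional form. The plan leaves open whether order is balanced or fully confounded with protocol for comfort, and that turns on an instruction that it does not contain. The bias is zero under a common quadrant order with 1:1 allocation and (2p-1)d when one protocol is completed first in a share p of participants. It reaches d, and cannot be corrected, when the same protocol is always first. The 0.5 to 1.0 point for that last case rests on an assumed effect of 0.25 to 0.5 point per position; the formula does not depend on those values. The change should be made, because it is cheap before treatment and the worst case cannot be repaired afterwards.

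**What to change.** 1. State one quadrant sequence for every participant, for example I, II, III, IV, and state 1:1 allocation. The existing randomisation then counterbalances protocol order. Alternatively, randomise the starting protocol within the same blocks.
2. Record the order actually used.
3. Name an analysis for comfort: the within-participant test-minus-control difference (mean of two test quadrants minus mean of two control quadrants), analysed as paired data with actual treatment order as a factor, in place of the unpaired Mann-Whitney test. Under the common sequence, order coincides with group A or B; under a randomised start it does not, so the recorded order must be used.
4. Give comfort a rank among the outcomes.
5. Optionally, add a 0-10 rating as each quadrant is finished and keep the end-of-session rating.

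The cost is a sentence or two in the protocol and plan and a line on the treatment form, plus short pauses if step 5 is adopted. There are two practical downsides: more switching between devices, and discloser and instructions that come before some control quadrants.

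The text is in the past tense. If treatment is complete, report the order used, adjust for it where it varied, and qualify the comfort conclusion if one protocol always came first.
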